9.3 SAEs or Serious SARs

9.3.1 Timing

After informed consent but prior to initiation of study medications, only SAEs caused by a protocol-mandated intervention will be collected (e.g. SAEs related to invasive procedures such as biopsies, medication washout).

For any other experience or condition that meets the definition of an SAE or a serious SAR, recording of the event must begin from day 1 of study treatment and continue through the 30-day follow-up period after treatment is discontinued.

9.3.2 Documentation and Notification

SAEs or Serious SARs must be documented and the NCCN project manager notified of the event/reaction via email within 24 hours of learning of its occurrence.

9.4 Adverse Event Reporting

9.4.1 IRB Reporting Requirements:

UNC:

- The UNC IRB will be notified of all SAEs that qualify as an Unanticipated Problem as per UNC IRB policy using the IRB's web-based reporting system within 7 days of the Investigator becoming aware of the problem. Please note, these events must be reported to the sponsor within 24 hours of learning of the occurrence.

Pregnancy:

- Pregnancies and suspected pregnancies (including a positive pregnancy test regardless of age or disease state) of a female subject occurring while the subject is on study, or within 30 days of the subject's last dose of study drug should be recorded as SAEs. The subject is to be discontinued immediately from the study.
- The female subject should be referred to an obstetrician-gynecologist, preferably one experienced in reproductive toxicity for further evaluation and counseling.

- The Investigator will follow the female subject until completion of the pregnancy and must document the outcome of the pregnancy (either normal or abnormal outcome) and report the condition of the fetus or newborn to the UNC study coordinator. If the outcome of the pregnancy was abnormal (e.g., spontaneous or therapeutic abortion), the investigator should report the abnormal outcome as an AE. If the abnormal outcome meets any of the serious criteria, it must be reported as an SAE.

9.5 Data and Safety Monitoring Plan

The study PI will provide continuous monitoring of subject safety in this trial with periodic reporting to the Data and Safety Monitoring Board (DSMB).

Meetings/teleconferences will be held at a frequency dependent on study accrual, and in consultation with the study Biostatistician. These meetings will include the investigators as well as protocol nurses, clinical research associates, regulatory associates, data managers, biostatisticians, and any other relevant personnel the study PI may deem appropriate. At these meetings, the research team will discuss all issues relevant to study progress, including enrollment, safety, regulatory, data collection, etc.

The team will produce summaries or minutes of these meetings. These summaries will be available for inspection when requested by any of the regulatory bodies charged with the safety of human subjects and the integrity of data including, but not limited to, the oversight Office of Human Research Ethics Biomedical IRB, the Oncology Protocol Review Committee (PRC) or the North Carolina TraCS Institute DSMB.

The UNC LCCC DSMB will review the study on a regular (quarterly to annually) basis, with the frequency of review based on risk and complexity as determined by UNC PRC. The study PI will be responsible for submitting the following information for review:

1. Safety and accrual data including the number of subjects treated
2. Significant developments reported in the literature that may affect the safety of participants or the ethics of the study
3. Preliminary response data
4. Summaries of team meetings that have occurred since the last report

Findings from the DSMB review will be disseminated by memo to the study PI, UNC PRC, and UNC IRB.

10.0 STATISTICAL CONSIDERATIONS

10.1 Study Design/Study Endpoints

This is a single arm, prospective, phase II clinical trial for safety and efficacy of risk-stratified treatment with rituximab +/- chemotherapy for MCD. Eligible patients will be enrolled and treated according to the study schema. High-risk patients (defined as patients with ECOG performance status >2 or hemoglobin <8 g/dL during screening or enrollment)^{9,10,13-16} will receive four weekly doses of rituximab (375 mg/m²) and etoposide

(100 mg/m²) as in Bower, et al.⁹ Note that patients with low hemoglobin within the last month that receive a blood transfusion as treatment will be considered high risk if their pre-transfusion hemoglobin was <8 g/dL. Low-risk patients will receive the same dose of rituximab alone. The planned sample size is 27 patients and the primary outcome is safety. Secondary outcomes include one- and two-year EFS (relapse, development of NHL, or death), OS, and KS exacerbation rates. We will also collect clinical, laboratory, virologic data, and stored samples at baseline and end-of-treatment to both describe the presentation of MCD in our population and to evaluate risk factors for death or relapse. Finally, we will conduct comprehensive microcosting analysis and a Markov model cost-effectiveness analysis.

10.2 Sample Size, Accrual and Duration of Accrual

To assess safety, toxicities will be monitored, graded, and documented by investigators at each clinic visit. Rituximab-based treatment will be considered safe in this population provided <40% non-hematologic AEs; we hypothesize that the true rate will be around 20%, based on previous studies.^{9,10,15,16} With a sample size of 24 patients, we reach 80% power to reject (if we observe $\leq 6 \geq$ Grade 3 AEs) the null hypothesis (H_0 : toxicity rate $>40\%$) using a one-sided exact test at $\alpha=0.1$. To account for 10% possible loss to follow-up during the toxicity-monitoring period, we will plan to enroll 27 patients. We plan to enroll approximately 10 patients annually and therefore expect to accrue patients for a total of three years.

10.3 Safety monitoring

Sequential boundaries will be used to monitor the rate of treatment-related mortality and non-hematologic AEs. Accrual to the study will be suspended until the study PI, co-investigators and the DSMC can review the data, and determine if the study should continue, be amended, or be closed to further accrual if excessive numbers of these events are seen (i.e., the number of deaths or the number of non-hematologic AEs is equal to or exceeds b_n out of n patients with full follow-up (**Table 8**)). The boundaries for treatment-related mortality rate are Pocock-type stopping boundaries that yield the probability of crossing the boundary at most 0.05 when the death rate is equal to the acceptable rate (0.10). The boundaries for the rate non-hematologic AEs are Pocock-type stopping boundaries that yield the probability of crossing the boundary at most 0.05 when the death rate is equal to the acceptable rate (0.40). The bounds are non-binding, and provide a guideline that may result in study modification or closure.

Table 8: Pocock-stopping bounds for deaths and adverse events.

Number of Patients, n	1	2	3	4	5	6	7	8	9	10	11	12	13	14	15	16	17	18	19	20	21	22	23	24
Boundary Treatment-related mortality, b_n	-	2	2	2	2	3	3	3	3	3	3	4	4	4	4	4	4	4	4	5	5	5	5	
Boundary Grade ≥ 3 non-hematologic adverse events b_n	-	-	-	-	5	6	6	7	8	8	9	9	10	10	11	11	12	13	13	14	14	15	15	

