1.3 Rituximab

Rituximab, an anti-CD20 monoclonal antibody, induces long-term remissions and decreases the risk of NHL in small clinical trials for MCD in HIC.^{9,10,16,30} Rituximab is a chimeric monoclonal antibody against CD20, a protein on the surface of B-cells which leads to B-cell depletion via complement- and antibody-mediated cytotoxicity. In two phase II trials of single-agent rituximab for MCD, the one-year event-free survival (EFS) was 92% and 71%.^{10,15} After longer follow-up, five-year EFS was 78% and five-year OS was 88%.³¹ Likewise, rituximab has been shown to significantly decrease the risk of NHL.^{9,30,31}

Mortality often occurs in the first month of treatment with rituximab monotherapy, but this risk can be mitigated with concomitant chemotherapy. Death in the first four weeks occurs in 5% of MCD subjects treated with rituximab alone.^{10,13-15,31} Risk factors for early death include ECOG performance status >2, hemophagocytic syndrome, and severe hemolytic anemia. The risk of death decreases with the addition of etoposide⁹ or liposomal

doxorubicin.¹⁶ Among subjects with MCD and pre-existing KS, the risk of KS exacerbation following rituximab monotherapy is 36-75%.^{9,10} However, death from KS progression is rarely reported.

Rituximab has not been evaluated as first-line therapy for MCD in SSA. Given high opportunistic infection burden and limited supportive care infrastructure in SSA, region-specific safety and efficacy data for rituximab are needed. When added to combination chemotherapy for NHL in HIC, rituximab has been associated with an increase in treatment-related infections and mortality in HIV-infected subjects with a CD4 count <50 cells/ μ l, while benefiting those with higher CD4 counts.^{32,33} Rituximab-based treatment +/- etoposide is likely to be less toxic than combination chemotherapy, but requires formal safety assessment. Previous studies of rituximab for MCD from HIC have found a rate of non-hematologic \geq Grade 3 AEs of around 20%.^{9,10,15,16}

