3.0 STUDY ENDPOINTS

3.1 Primary Endpoint

Safety will be classified and graded by non-hematologic Grade ≥ 3 AEs (CTCAE v5.0) and treatment-related mortality through twelve weeks from the start of rituximab with or without etoposide therapy.

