5.8 Duration of Follow Up

For determination of study endpoints, all subjects will be followed for up to 24 months or until death, whichever occurs first after removal from study treatment.

Subjects removed from study treatment for unacceptable AEs will be followed for resolution or stabilization of the AE(s). All subjects (including those withdrawn for AEs) should be followed after removal from study treatment as stipulated in the protocol.

Although study follow-up is for 24 months, patients will be consented to be contacted at 30, 36, 42, 48, 54, and 60 months simply to assess vital status after completion of study procedures.

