8.3 Assessment of Safety

Any subject who receives at least one dose of study therapy on this protocol will be evaluable for toxicity. Each subject will be assessed periodically for the development of any toxicity according to the Time and Events table. Toxicity will be assessed according to the NCI CTCAEv5.0.

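### Table 8 counts only patients with an undefined full follow-up; read as 12 weeks, pauses come about 1.5 patients later than needed

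*Combined protocol and SAP*

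**What the plan says.** Section 10.3 (Safety monitoring) pauses accrual for review when treatment-related deaths or non-hematologic AEs reach a count that "is equal to or exceeds b_n out of n patients with full follow-up". It does not say what full follow-up is, when an event enters the count, or how a patient who has an event and is then lost is treated. It states a crossing probability of at most 0.05 at acceptable rates of 0.10 (deaths) and 0.40 (AEs), and calls the bounds non-binding.

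Other sections bear on the missing definition:

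- Section 3.1 sets the primary window: "treatment-related mortality through twelve weeks from the start of rituximab with or without etoposide therapy".
- Section 5.8 uses a longer horizon: "all subjects will be followed for up to 24 months or until death".
- Sections 9.2 and 9.3.1 record AEs and SAEs until 30 days after treatment is discontinued.
- Section 8.3 does not require completed follow-up: "Any subject who receives at least one dose of study therapy on this protocol will be evaluable for toxicity".
- Section 10.2 enrolls 27 to obtain 24: "To account for 10% possible loss to follow-up during the toxicity-monitoring period".

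**The concern.** The trigger exists to limit how many patients enter while a safety signal is building. Section 1.3 reports that "Mortality often occurs in the first month of treatment with rituximab monotherapy", and the last planned dose is on day 22 (section 5.2, Table 1), so many events would be known weeks before week 12. If the trigger waits for week 12, accrual continues on information already in hand.

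Loss adds a second issue. Section 10.5.2 cites a strong association between loss to follow-up and death and counts loss as failure for EFS and OS. The safety trigger, read literally, can leave those same patients out. Two readers could therefore run Table 8 differently on the same data.

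**Working it through.** **Inputs from the documents.** Accrual about 10 per year, 27 enrolled for 24, 10% loss (10.2); 12-week window (3.1); doses on days 1, 8, 15 and 22 (5.2); Table 8 (10.3). As extracted, each row shows 23 values under 24 columns, so b_n was applied at n = 1–23.

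**Assumptions not in the documents.** Poisson accrual; events on days 1–35; loss time uniform over the window.

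**1. The plan's own figures.** With f_n(k) the probability of k events in n patients without an earlier crossing, f_n(k) = (1−p)·f_{n−1}(k) + p·f_{n−1}(k−1); mass at k ≥ b_n is removed and summed.

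- AE row at p = 0.40: 0.049. The stated limit of 0.05 reproduces.
- Mortality row at p = 0.10: 0.185, or 0.190 with a further 5 at n = 24. The stated 0.05 does not reproduce. This is a separate error.
- Final rule (≤6 of 24): 0.096 at 40% and 0.811 at 20%. Also 24/0.9 = 26.7, so 27. These reproduce.

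**2. Rough size of the delay.** The mean event day is (1+35)/2 = 18.

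- Waiting until day 84 costs 66 days: 66/365 × 10 = 1.8 patients.
- If follow-up ends 30 days after the last dose (day 22+30 = 52), the wait is 34 days: 34/365 × 10 = 0.9 patients.

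**3. Why an earlier check need not add pauses.** Suppose recorded events among all N dosed patients have reached b_N and nobody is lost. Once those N complete follow-up, the count at n = N is at least b_N, so the existing rule must cross by then. Pausing at once changes only the date.

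**4. Simulation, 12-week window, no loss** (6,000 trials per scenario):

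| Row and true rate | Pause probability, either rule | Mean enrolled at pause: existing rule | With all-dosed check |
|---|---|---|---|
| Mortality 20% | 0.64 | 12.1 | 10.4 |
| Mortality 30% | 0.92 | 10.3 | 8.6 |
| AE 60% | 0.50 | 14.7 | 13.2 |

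The differences are 1.7, 1.7 and 1.5 patients; repeat runs gave 1.4–1.7, and pauses about 8–9 weeks earlier. At an AE rate of 40% both rules give about 0.05.

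With a 52-day window the saving is 0.8–0.9 patients on the mortality row (20%: 11.1 to 10.3) and about 0.7 on the AE row (60%: 13.7 to 13.0).

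As a check on the event-time assumption, counting in enrolment order and entering each event when seen brings the pause about 5 weeks and 1 patient forward if events are uniform over 12 weeks. If they fall in the first 4 weeks, it is about 10 weeks and 1.9 patients.

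**5. Loss of 10%, unrelated to events.**

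- Existing rule: AE-row detection at 60% is 0.51 with no loss and 0.50 with 10% loss. Lost patients leave numerator and denominator together.
- All-dosed check added: enrolment at the pause falls from 12.8 to 10.9 (20% mortality). Pause probability rises from about 0.19 to 0.21–0.22 (mortality row, 10%) and by under 0.01, to about 0.047–0.058 (AE row, 40%).
- All-dosed check alone: AE detection at 60% is 0.40–0.47, below the existing 0.50. Both checks are needed.

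**6. Loss linked to events.** The documents give no size. As an illustration, with loss twice as likely after an event, the existing rule pauses with probability about 0.56 at 20% mortality, against 0.63 with the added check.

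**7. A version to avoid.** Comparing all recorded events with b_n at n = completed patients raises the AE-row pause probability at 40% from 0.05 to about 0.30 with no loss and 0.36–0.39 with 10% loss. Keeping lost patients only when they had an event gives 0.06–0.08.

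**The case against.** The case against acting is reasonable. The bounds are non-binding, the study PI monitors safety continuously with DSMB reports (9.5), and SAEs are notified within 24 hours (9.3.2), so nobody has to wait for Table 8. The gain is one to two patients, and only in trials that pause. This limits the size of the point. It does not remove it, because Table 8 is the only numerical trigger for suspending accrual.

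A reader might also infer more than the documents support:

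- *That events in lost patients never count.* This is one reading of an undefined term, and section 8.3 points the other way.
- *That a patient who dies early can never be counted, so the mortality row cannot work.* Section 5.8 ends follow-up at death, so a death can be read as completing it.
- *That 12 weeks is the stated window of the trigger.* It is inferred from 3.1. The 30-day recording period in 9.2 and 9.3.1 roughly halves the saving, and the 24 months of 5.8 would make the rule slower.
- *That loss as such biases the trigger.* Under-detection needs loss linked to events.
- *That the earlier check is free.* That holds only with no loss. With the planned 10% the AE row can pass 0.05.

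**Conclusion.** The concern holds in limited form. Section 10.3 ties its trigger to an undefined set of patients that does not sit easily with section 8.3. Under the 12-week reading, with accrual of 10 per year and events in days 1–35, pauses come about 1.5 patients later than needed, and with no loss the delay buys no reduction in false pauses. Under a 30-day reading the delay is about 0.8–0.9 patients on the mortality row.

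With loss unrelated to events the rule is late but essentially unbiased. With linked loss, which section 10.5.2 makes plausible for deaths, detection also falls, by an amount the documents do not allow one to fix. This is worth correcting because the correction is cheap, not because the present rule fails to protect patients.

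**What to change.** In section 10.3:

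1. Define full follow-up, including whether death or a qualifying event completes it, and reconcile it with 3.1, 5.8 and 8.3 and with the recording period in 9.2 and 9.3.1.
2. Keep the present check, with the same completed patients in numerator and denominator. State that all recorded events are never set against completed patients only.
3. Add a second check: suspend accrual as soon as recorded events among all N dosed patients, including those later lost, reach b_N, with all N in the denominator. Give b_N for N = 25–27 too, since Table 8 stops at 24 and 27 are planned.
4. Recompute the crossing probabilities of the combined rule at the planned 10% loss against the stated 0.05. Correct the mortality row at the same time, since its crossing probability is already about 0.18–0.19 at a 10% rate.

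The cost is a few sentences and one recalculation, with no extra patients, visits or data. The downside is the slightly higher pause probability under loss shown above, which the recalculation should report and, if needed, remove by adjusting the bounds.

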10.4 Data Analysis Plans

10.4.1 Primary Objective: To describe the safety, as determined by the rate of Grade ≥ 3 non-hematologic AEs and treatment-related mortality, of a risk-adjusted approach to the treatment of MCD with rituximab (375 mg/m² weekly for four weeks) +/- etoposide (100 mg/m² weekly for four weeks) in Malawi.

The rate will be estimated for individual AEs and a summation of Grade ≥ 3 non-hematologic AEs will be estimated along with a 95% confidence interval.

The rate of treatment-related mortality will be estimated along with a 95% confidence interval around the point estimate.

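### Table 8's treatment-related mortality row crosses with probability about 0.19 at a 10% death rate, not the stated limit of 0.05

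*Combined protocol and SAP*

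**What the plan says.** Section 10.3 sets sequential bounds for two event types, treatment-related deaths and non-hematologic adverse events (AEs). A bound is crossed when the count "is equal to or exceeds b_n out of n patients with full follow-up", and Table 8 has one column for every n from 1 to 24. On a crossing, "Accrual to the study will be suspended until the study PI, co-investigators and the DSMC can review the data".

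For deaths the section states the operating property: "The boundaries for treatment-related mortality rate are Pocock-type stopping boundaries that yield the probability of crossing the boundary at most 0.05" when the true death rate is 0.10. A parallel sentence claims the same 0.05 limit for the AE row at a rate of 0.40.

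The section adds: "The bounds are non-binding, and provide a guideline that may result in study modification or closure". Section 10.4.1 then treats mortality by estimation only: "The rate of treatment-related mortality will be estimated along with a 95% confidence interval around the point estimate".

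**The concern.** A Pocock-type rule that crosses with probability at most 0.05 over the whole trial cannot include any look where meeting the bound is by itself more likely than 0.05. The mortality row sets the bound at 2 deaths through n=5. At a 10% death rate, two or more deaths among five patients has probability 0.081, so the stated limit is already broken at that column.

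Table 8 is the plan's numeric trigger for pausing accrual on treatment-related mortality, which is part of the primary endpoint. The people reviewing data after a crossing will read it against the stated property. They would take two deaths in the first five patients as something with less than a 1 in 20 chance over the whole trial at an acceptable rate, when the printed row gives nearly 1 in 5. With about 10 patients planned per year (Section 10.2), an unplanned pause is costly.

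**Working it through.** **Inputs** (Section 10.3 and Table 8)

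- Mortality row, read left to right: no bound at n=1; 2 at n=2–5; 3 at n=6–11; 4 at n=12–19; 5 at n=20–23. The text shows 23 entries under 24 columns, so b_24 is not visible.
- AE row: no bound at n=1–4; then 5, 6, 6, 7, 8, 8, 9, 9, 10, 10, 11, 11, 12, 13, 13, 14, 14, 15, 15 at n=5–23.
- Acceptable rates: 0.10 (deaths) and 0.40 (AEs). Claimed crossing probability for each: at most 0.05.

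**Method.** Let f_n(k) be the probability of k events in n patients with no earlier crossing. Then f_n(k) = (1−p)·f_{n−1}(k) + p·f_{n−1}(k−1). At each n, the probability at k ≥ b_n is removed and added to the crossing total. Patients are taken as independent, each with at most one counted event.

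**Step 1: reproduce the plan's figure where it can be reproduced.** The AE row at p=0.40 gives 0.049 over n=1–23, which agrees with the claim. Rebuilding a Pocock-type row (one constant single-look tail level, as large as the 0.05 limit allows) returns all 23 printed AE entries. This supports both the patient-by-patient reading and the left alignment of the columns.

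**Step 2: a hand check on the mortality row.** The bound is 2 from n=2 to n=5, so crossing by n=5 is the same as two or more deaths in five patients:

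1 − 0.9^5 − 5(0.1)(0.9^4) = 1 − 0.59049 − 0.32805 = 0.0815.

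**Step 3: the whole mortality row at p=0.10.**

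| n | cumulative crossing probability |
|---|---|
| 2 | 0.010 |
| 3 | 0.028 |
| 4 | 0.052 |
| 5 | 0.081 |
| 11 | 0.128 |
| 19 | 0.177 |
| 23 | 0.185 |

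The ratio to the stated limit is 0.185/0.05 = 3.7. The share reached by n=5 is 0.0815/0.1851 = 44%.

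**Step 4: the missing cell.** With b_24 absent or 6 the total is 0.185; with b_24=5 it is 0.190. Moving the whole row one column right raises it to 0.220, but the same move takes the AE row to 0.098, so that alignment is unlikely. No placement of the missing entry gives less than 0.185.

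**Step 5: single looks.** At p=0.10, P(X ≥ b_n) exceeds 0.05 in 13 of the 22 printed mortality cells (n=4, 5, 9–11, 15–19, 21–23); for example 0.090 at n=11 and 0.115 at n=19. The largest value in any AE cell at p=0.40 is 0.019.

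**Step 6: other death rates** (printed cells only).

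| death rate | crossing probability |
|---|---|
| 5% | 0.038 |
| 6% | 0.058 |
| 8% | 0.113 |
| 10% | 0.185 |
| 15% | 0.414 |
| 20% | 0.643 |

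The total equals 0.05 at a death rate of about 5.6%.

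**The case against.** The best defence is that little turns on this. The row errs towards stopping too readily, the bounds are guidelines, and a crossing leads to a review that may end with the study continuing. Section 9.5 adds continuous monitoring by the investigator and regular board review. The primary test in Section 10.2 rests on AEs, and mortality is only estimated. All of that stands and limits the consequence. It does not alter the probability of crossing, which is what the sentence states.

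A second defence is that looks may be sparser than every patient. Some schedules do comply: n=20 alone gives 0.043, and n=6 and 12 give 0.033. Others do not: n=10 and 20 gives 0.089, and n=6, 12 and 18 gives 0.102. The plan names no schedule for these bounds, and Table 8 gives a bound for nearly every n.

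A third point qualifies the comparison with the AE row. Its 0.049 holds through n=23, or with b_24=16; if the unseen cell were 15, the total would be 0.054. It also assumes that patients with an event are counted, whereas Section 10.3 speaks of the number of AEs. The AE row is therefore consistent as printed and on that counting rule. The mortality result is unaffected.

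**Conclusion.** The concern holds. As printed, the mortality row crosses with probability 0.185 to 0.190 at the acceptable rate of 0.10, against a stated limit of 0.05. This assumes a look after each patient with full follow-up, independent patients, and the columns as printed; no placement of the missing 24th entry brings the figure down to 0.05.

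The text and the table imply different acceptable rates: 10% in the sentence, about 5.6% in the row. A row built for a lower rate is plausible: among the rates tried, a Pocock-type row for 6% came closest, matching 21 of the 23 entries. That is only an inference, and the documents do not show which element was intended.

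This should be fixed, but it is not critical. The practical harm is a misread or unplanned accrual pause rather than missed deaths.

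**What to change.** The study team should decide which of the row, the 0.10 rate and the 0.05 limit is intended, and make the other two agree.

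- **Option A: keep the row and correct the sentence.** State that it crosses with probability about 0.19 at a 10% death rate and about 0.04 at 5%. This is wording only; monitoring does not change.
- **Option B: keep 0.05 at 10% and recompute the row.** To illustrate what that property implies for 24 looks (not as a recommended rule), a Pocock-type row would be 2 at n=2, 3 at n=3–6, 4 at n=7–11, 5 at n=12–17, 6 at n=18–22 and 7 at n=23–24, crossing with probability 0.0495 at 10%. The cost is sensitivity: crossing falls from 0.41 to 0.17 at a 15% death rate and from 0.64 to 0.36 at 20%. The sponsor and the monitoring board would have to accept that knowingly.

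Under either option, fill in or explain the n=24 cell, and state the look schedule with the bounds if looks are meant to be less frequent than every patient. At the same time, correct the AE sentence, which calls the 0.40 rate a death rate, and say that the AE bound counts patients with an event. The printed AE values through n=23 need no change.
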